8.4.1 Cohort and Follow-up Periods for Sieve Analysis

All sieve analyses will be conducted in the ATP cohort with (i) follow-up through 12 months post-Dose 3, and (ii) follow-up through 24 months post-Dose 3 (i.e., the same cohort and follow-up periods as in the primary analyses). Both study site-specific and study site-pooled analyses will be performed.

8.4.2 Sieve Analysis for Primary Endpoint 1

The methods assess genotype-specific (relative) vaccine efficacy and evaluate differential (relative) vaccine efficacy (i.e., the so-called sieve effect) against primary endpoint 1.

The following sieve analysis methods will be applied that assume a single haplotype, observed or missing, per case (with multiple outputation added for haplotype-specific sequence features (a)–(d)):

For the binary haplotype-level features in (a)–(c), we will estimate genotype-specific hazard-ratio (relative) VE with 95% CIs and a two-sided test for differential genotype-specific (relative) VE using the methods proposed in the yet unpublished manuscript Heng, Sun, and Gilbert, “Estimation and hypothesis testing of strain-specific vaccine efficacy with missing strain types with applications to a COVID-19 vaccine trial” and implemented in the R package *cmprskPH*. This method accommodates missing sequences by augmented IPW.

For the Hamming distance feature in (d), the genotype-specific hazard-ratio (relative) VE, defined as one minus the genotype-specific hazard ratio (vaccine/control), will be assessed in the ATP cohort using the genotype-specific hazard-ratio model for either fully observed genotypes (Juraska and Gilbert, 2013; implemented in the R package [*sievePH*](#)) or for partially missing genotypes using inverse-probability weighting (IPW) or augmented IPW (AIPW) (Juraska and Gilbert, 2016; implemented in [*sievePH*](#)), stratified by study site (for the study site-pooled analysis only) and adjusted for predictors of new malaria infection. We will use the IPW or AIPW version of the analysis method for amplicon-specific genotypes that are continuous or count variables and the standard version for COI which is an aggregate measure across both amplicons. For each ATP cohort analysis in Table 2 comparing vaccine to control, plus comparing vaccine arms GP2–GP4 pooled to control, inference will include 95% pointwise Wald CIs for genotype-specific VE and a Wald test of the null hypothesis that VE is invariant with respect to the AA sequence feature. For each ATP cohort analysis in Table 2 comparing two vaccine regimens head-to-head, the same inference will be reported except on the hazard ratio scale.

One-sided testing will be performed for comparisons to the control GP1 regimen of 3D7 Hamming distances, and two-sided testing will be performed for head-to-head RTS,S regimen comparisons of 3D7 Hamming distances as well as for all comparisons of all other quantitative sequence features. Statistical significance is defined as in Section 7.8 except, for multiplicity sets in which one-sided testing is performed, the same definition of FWER and FDR statistical significance is applied to doubled one-sided p-values.

We will also apply the cumulative incidence-based sieve analysis methodology of Benkeser, Juraska, and Gilbert (2020), extended to accommodate missing sequence data under a missing at random assumption. These methods treat the Hamming distance of an infecting parasite to the 3D7 vaccine strain as a count variable. For applications of the method where the distance is continuous (or nearly so) rather than a count variable, the Benkeser, Juraska, Gilbert et al. methodology will be applied binning the continuous values onto a grid.

8.4.3 Multiple Hypothesis Testing Adjustment for Sieve Analysis for Primary Endpoint 1

To minimize the occurrence of false positive sieve effect results given the large number of analyzed sequence features and group comparisons and thereby increase the credibility of the sieve analysis, it is critical to use a stringent multiplicity adjustment for hazard-based sieve tests. To this end, q-values controlling the false discovery rate and

Holm-Bonferroni-adjusted p-values controlling the familywise type 1 error rate will be used, applied in the analyses of follow-up data through the Month 20 visit separately to the following multiplicity sets defined by combinations of a group comparison with a set of features:

- GP2–GP4 vs. GP1 by 3D7 residue match/mismatch features in all screened-in CS C-terminus haplotypic regions and CS C-terminus AA positions
- GP2+GP3 vs. GP1 by 3D7 residue match/mismatch features in all screened-in CS C-terminus haplotypic regions and CS C-terminus AA positions
- GP4 vs. GP1 by 3D7 residue match/mismatch features in all screened-in CS C-terminus haplotypic regions and CS C-terminus AA positions
- GP5 vs. GP1 by 3D7 residue match/mismatch features in all screened-in CS C-terminus haplotypic regions and CS C-terminus AA positions
- GP4 vs. GP2+GP3 by 3D7 residue match/mismatch features in all screened-in CS C-terminus haplotypic regions and CS C-terminus AA positions
- GP2–GP4 vs. GP1 by 3D7 Hamming distance in all CS C-terminus haplotypic regions
- GP2+GP3 vs. GP1 by 3D7 Hamming distance in all CS C-terminus haplotypic regions
- GP4 vs. GP1 by 3D7 Hamming distance in all CS C-terminus haplotypic regions
- GP5 vs. GP1 by 3D7 Hamming distance in all CS C-terminus haplotypic regions
- GP4 vs. GP2+GP3 by 3D7 Hamming distance in all CS C-terminus haplotypic regions
- GP2–GP4 vs. GP1 by 3D7 residue match/mismatch features in all screened-in SERA2 AA positions
- GP2+GP3 vs. GP1 by 3D7 residue match/mismatch features in all screened-in SERA2 AA positions
- GP4 vs. GP1 by 3D7 residue match/mismatch features in all screened-in SERA2 AA positions
- GP5 vs. GP1 by 3D7 residue match/mismatch features in all screened-in SERA2 AA positions
- GP4 vs. GP2+GP3 by 3D7 residue match/mismatch features in all screened-in SERA2 AA positions

Multiplicity adjustment will be applied separately in the study site-pooled and each study site-specific analysis. In the analyses of data through the Month 32 visit, comparisons involving GP2 and GP3 will be performed separately, i.e., the full set of group comparisons will be: GP2–GP4 vs. GP1, GP2 vs. GP1, GP3 vs. GP1, GP4 vs. GP1, GP5 vs. GP1, GP3 vs. GP2, GP4 vs. GP2, GP4 vs. GP3.

No multiplicity adjustment will be applied to COI and the other complexity indices.

Statistical significance is defined the same as in Section 7.8 with one-sided p-values doubled before multiplicity adjustment is performed.

8.4.4 Sieve Analysis for Primary Endpoint 2

Accounting for all data on new malaria infections collected during a given specified follow-up period, the three “active surveillance” versions of the Follmann and Huang (2018) methods specified in the last two columns of Table 3 of their paper will be applied to address different questions, as explained in Follmann and Huang. Here we specify the details of how the variables and models are defined to assess genotype-specific vaccine efficacy and genotype-specific relative vaccine efficacy, for each of the genotype features defined above.

The two Follmann and Huang methods that are applied are the “product method on X_f ” and the “product method on $I(X_f > 0)$ ” method. Here X_f for a given participant denotes $X_f = X_{1f} + \dots + X_{Cf}$, where C is the number of new malaria infections (i.e., primary endpoint 2) and X_{cf} is the number of sequences from the c^{th} new malaria infection that have haplotype f . Both methods are applied assuming model (5) in Follmann and Huang, where the regression coefficient β is estimated using standard Cox model software, which is fit adjusting for the same baseline covariates adjusted for in the primary analyses of primary endpoint 2, and also adjusting for study site for the analyses that pool over study sites. In addition to assuming model (5), the product method on X_f also assumes model (6) of Follmann and Huang, and yields point and 95% CI estimates of VE_{Mf} defined in Follmann and Huang. The product method on $I(X_f > 0)$ assumes model (7) of Follmann and Huang (in addition to model (5)) and yields point and 95% CI estimates of VE_{If} defined in Follmann and Huang. For inferences about differential VE by two haplotypes $f=1$ vs. $f=2$, the methods also provide point and 95% CI estimates for Follmann and Huang’s differential VE parameters: $\exp(\alpha_{2M}) = (1 - VE_{M1})/(1 - VE_{M2})$ and $\exp(\alpha_{2I}) = (1 - VE_{I1})/(1 - VE_{I2})$, as well as providing Wald 2-sided p-values for sieve effects, where the product method on X_f tests $H_0: \alpha_{2M}=0$ and the product method on $I(X_f > 0)$ testing $H_0: \alpha_{2I}=0$.

As for other analyses, the analyses are done for each study site separately as well as pooling the two study sites.

8.5 Analytic Approach for Exploratory Objective 2

8.5.1 Summary of Modeling Approach for Exploratory Objectives 2 and 3

A flexible dynamic model of multiple types of recurrent events will be applied to address exploratory objectives 2 and 3. To express the model, let $T_{i,k,j}$ be the j^{th} type- k event of participant i , $0 \leq T_{i,k,1} < T_{i,k,2} < \dots < T_{i,k,n_{ik}} \leq \tau$, where n_{ik} is the total number of type- k events for participant i . Let $N_{ik}^*(t)$ be the counting process registering the number of type- k recurrent events for individual i in the time interval $[0, t]$, for $k = 1, \dots, K$ and $i = 1, \dots, n$. Let $Y_i(t) = I(C_i \geq t)$ be the at-risk process and $N_{ik}(t) = \int_0^t Y_i(s) dN_{ik}^*(s)$ be the process registering numbers of observed type- k events, where C_i is the right censoring

time. Let \mathcal{F}_t represent the event history for all participants up to time t . The intensity of $N_{ik}(t)$ is given by P .

We consider the following dynamic semiparametric model for the intensity:

$$\lambda_{ik}(t) = \lambda_{k0}(t) e^{\beta_k^T(t)X_i(t) + \gamma_k^T(U_i(t))Z_i(t)}$$

for $k = 1, \dots, K$, where $\lambda_{k0}(t)$ is an unspecified baseline function, and $\beta_k(\cdot)$ is a vector of unspecified functions that represents possibly time-varying effects of covariates $X_i(t)$, and $\gamma_k(\cdot)$ is a vector of unspecified functions that represents effects of covariates $Z_i(t)$ that can depend dynamically on exposure variables $U_i(t)$ over time such as past malaria infections. The covariates $X_i(t)$ of interest include baseline covariates to adjust for and treatment assignment to RTS,S vaccination vs. control.

The coefficient function $\beta_k(t)$ is the log relative risk corresponding to the increase in the intensity of having a new malaria infection of type k at time t for every one unit increase in the covariate $X_i(t)$. The coefficient function and $\gamma_k(u)$ is the log relative risk corresponding to the increase in the intensity of having a new malaria infection of type k at time t and u unit time since the last new infection or vaccination for every one unit increase in the covariate $Z_i(t)$.

Setting $Z_i(t) = 1$ specifies an analysis of interest, in which case and $\gamma_k(u)$ is the log-scale increase in the intensity of having a new malaria infection of type k at time t and u unit time since the last new infection or vaccination. When and $\gamma_k(u)$ is positive, $\exp(\gamma_k(u))$ exceeds one and corresponds to a relative intensity (instantaneous relative risk) increasing with time since the last new infection or vaccination.

We can consider $U_i(t) = (U_{i1}^T(t), \dots, U_{iK}^T(t))^T$ as the part of the multi-type event history that could affect the intensity $\lambda_{ik}(t)$, where $U_{ik}(t)$ is related to the type- k event history of subject i . For example, choosing $U_{ik}(t) = (N_{ik}(t^-), t - T_{i,k,N_{ik}(t^-)})^T$ specifies the number of new infections molecularly detected between enrollment and time t (i.e., $N_{ik}(t^-)$ is the molecular force of infection mol[FOI] of strain k by time t for subject i) and the time since the last occurrence of molecularly detected strain k malaria infection, respectively. Specifying $\gamma_k(U_i(t)) = \eta_{kk}(t - T_{i,k,N_{ik}(t^-)})$ models time-varying effects since the last strain k infection, and specifying $\gamma_k(U_i(t)) = \eta_{kj}(t - T_{i,k,N_{ij}(t^-)})$ models how the time since the last strain j infection impacts time-varying effects on the intensity of strain k infection. In this notation $\eta_{kj}(t - T_{i,k,N_{ij}(t^-)})$ is a nonparametric function of $(t - T_{i,k,N_{ij}(t^-)})$.

The new infection event time variable is the same as used for the primary analyses, and the right-censoring time variable is modified. Specifically, the right-censoring time is defined as the last observed visit time (scheduled or unscheduled) before three consecutive missed scheduled visits with no intervening unscheduled visits. We selected three consecutive visits to define censoring based on a treatment-arm pooled descriptive analysis comparing several potential right-censoring definitions based on 2, 3, 4, 5, or 6 consecutive missed visits, where the percentage right-censoring was

45.3%, 29.5%, and 25.4% under the 2, 3, and 4 consecutive missed visits definitions of right-censoring, respectively.

To handle intermittent missed visits prior to right-censoring, we take advantage of the fact that the method flexibly allows subject-specific visit schedules.

Sensitivity analyses may be done that consider a new definition for the new infection event time variable (in terms of the sequence read-count criterion for defining a new malaria infection); if this is done the same new variable studied as a sensitivity analysis to the primary analysis will be studied.

8.5.2 Application of the modeling approach to address Exploratory Objective 2

Analyses for exploratory objective 2 are done in the TVC cohort only and studying new molecularly detected infection events during the M0-20 and M0-32 follow-up periods. Exploratory objective 2 applies the above-specified model counting all new malaria infection endpoints regardless of type k: thus the model is applied with a single k=1. We will study how does all-strain malaria infection risk depend on the molecular force of infection $N_i(t^-)$ and on time since most recent infection, as well as studying whether the effect of the molecular force of infection is modified by prior RTS,S vaccination.

Analysis 1. The model is first applied using the control arm participants only and with $X_i(t)$ consisting of (1) the baseline covariates study site (Siaya or Agogo), age at enrollment, and sex, and (2) the time-dependent covariate $N_i(t^-)$, with $\beta_1(t)$ and $\beta_2(t)$ time-dependent effects. In addition, the model specifies $\gamma(U_i(t)) = h(t - T_{i,N_i(t^-)})$. Estimation of the coefficient $\beta_2(t)$ in front of the $N_i(t^-)$ covariate assesses whether and how much the molecular force of infection up until time t impacts the intensity of new infection, after covariate adjustment. Estimation of the coefficient function $h(t - T_{i,N_i(t^-)})$ assesses how the time since the last new malaria infection impacts the intensity of new malaria infection, after covariate adjustment.

Analysis 2. The above analysis is repeated for all of the RTS,S vaccine arms pooled together.

Analysis 3. Analysis 3 repeats Analysis 2, again restricting to the RTS,S vaccine arms pooled, except now using $\gamma(U_i(t)) = h(t - S_{i,V_i(t^-)})$ where $V_i(t)$ is the counting process of vaccination times $\{S_{ij}\}$ and $t - S_{i,V_i(t^-)}$ is the time since the most recent vaccination. Estimation of the function $h(t - S_{i,V_i(t^-)})$ in this model assesses how the recency of a vaccine dose impacts the intensity of malaria infection.

Analysis 4. Analysis 4. applies the model to study whether and how time-varying VE against all-strain infection depends on the time since the last occurrence of infection. Similar to Analysis 2., all randomization arms are included in the analysis, and Z_i is the indicator that participant i was randomly assigned to an RTS,S vaccination arm.

8.6 Analytic Approach for Exploratory Objective 3

As for exploratory objective 2, analyses for exploratory objective 3 are done in the TVC cohort only and studying new molecularly detected infection events during the M0-20 and M0-32 follow-up periods.

The set of haplotypes k that are studied for exploratory objective 3 is the same set of haplotypes that are screened-in for the sieve analysis exploratory objective 1. In addition, sufficiently prevalent SERA2 haplotypes k may also be studied with exploratory objective 3.

Each of the four analyses described for exploratory objective 2 are repeated for each haplotype k . As always, the genotype categories are defined based on treatment-blinded analysis. For each defined genotype category, the four specified analyses are conducted.

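### Analysis 4 gives controls no term for time since last infection, so a recency effect shared by both arms would be read as VE varying with time since infection

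*SAP*

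**What the plan says.** SAP Section 8.5.1 writes the intensity of new infection as a baseline function times the exponential of two parts: β(t)'X(t) and γ(U(t))'Z(t). The second part holds effects of Z "that can depend dynamically on exposure variables" U, such as infection history. The covariates X "of interest include baseline covariates to adjust for and treatment assignment to RTS,S vaccination vs. control"; time since last infection is not among them. Setting Z = 1 is described as one analysis of interest, and γ(u) is then the recency effect in everyone analysed.

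Section 8.5.2 applies this model four times:

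- **Analysis 1:** "The model is first applied using the control arm participants only". X holds site, age, sex and N(t−), the number of earlier infections. A function h of time since last infection "assesses how the time since the last new malaria infection impacts the intensity of new malaria infection".
- **Analysis 2:** the same model in the pooled RTS,S arms.
- **Analysis 3:** RTS,S arms again, with time since last vaccination.
- **Analysis 4:** studies "whether and how time-varying VE against all-strain infection depends on the time since the last occurrence of infection". For this, "all randomization arms are included in the analysis, and Z_i is the indicator that participant i was randomly assigned to an RTS,S vaccination arm". The sentence likens this to Analysis 2, which has no control arm.

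Section 8.6 then says: "Each of the four analyses described for exploratory objective 2 are repeated for each haplotype k".

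**The concern.** To ask whether VE depends on time since infection, vaccinated and control children must be compared at the same time since infection. Analysis 4 as written does not do this. Controls have Z = 0, so their fitted intensity at study time t is the same whether their last infection was two weeks or a year ago. Vaccinated children at time u since infection are compared with all controls at risk at t. This is an interaction fitted without its main effect.

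The SAP itself allows that recency may matter apart from the vaccine. Analysis 1 estimates that effect in controls alone, and Section 7.1 says that antimalarial treatment may lower the risk of a new infection for a time. Such an effect, if shared by the arms, would appear in Analysis 4 as VE rising or falling after an infection even if VE were constant. Section 8.6 repeats the problem for each haplotype.

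**Working it through.** **Inputs from the documents.** The intensity model (SAP 8.5.1). Z as the RTS,S indicator (8.5.2, Analysis 4). N(t−) in X (8.5.2, Analysis 1). 300 children per group (Section 2), so 300 controls and 4 × 300 = 1,200 RTS,S recipients. Follow-up M0–20 in the TVC (8.5.2). The SAP gives no power or event figure for Analysis 4, so there is none to reproduce.

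**Algebra.** Let R be the RTS,S indicator. As written:

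- control: λ0(t) exp{β'X}
- RTS,S: λ0(t) exp{β'X + γ(u)}

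Suppose the truth is a shared recency effect f(u) and constant VE, that is, λ0(t) exp{f(u) + R log(1 − VE)}. The fitted baseline absorbs the control average of exp f, called m. Then approximately

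apparent VE(u) = 1 − (1 − VE) exp{f(u)} / m.

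The shape of f is read as the shape of VE. If f is zero, m = 1 and there is no bias. Treatment in X does not help, because controls still have no u term.

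**Simulation.** Assumed: control rate 0.10 infections per month, true VE 30% at every u, and the same recency effect in both arms. The fit is a discrete-time proportional hazards model with a free monthly baseline, at 20 times trial size. VE (%) is shown for children with no infection yet / 1–2 / 3–5 / ≥6 months since infection, with N(t−) in X:

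| Assumed effect | As written | Shared recency function added |
|---|---|---|
| None | 30.2 / 31.9 / 30.4 / 31.3 | 30.9 / 32.1 / 28.8 / 30.7 |
| Risk halved for 2 months | 27.8 / 60.4 / 20.9 / 23.2 | 30.9 / 27.3 / 28.9 / 30.7 |
| Risk doubled for 2 months | 36.9 / −11.7 / 43.0 / 42.4 | 31.0 / 30.8 / 28.5 / 31.0 |
| Risk ×1.5, then ×1.25 | 34.8 / 11.4 / 24.5 / 40.6 | 31.0 / 30.1 / 27.3 / 31.4 |
| No causal effect; frailty variance 0.5 | 30.2 / 17.8 / 18.6 / 17.2 | 25.8 / 21.1 / 20.8 / 23.6 |

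**Check of the formula.** Without N(t−), the halved-risk case gave 23.7 / 62.2 / 23.9 / 24.5. From 62.2%, 0.7 × 0.5 / m = 0.378, so m = 0.926. The formula then predicts 1 − 0.7 / 0.926 = 24.4% in the other intervals, which agrees.

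**Test of constant VE at trial size** (200 replicates, 5% level, true VE constant). As written, it rejects in 6.5% with no recency effect, 100% with halved risk and 99% with ×1.5 then ×1.25. With the shared function, it rejects in 5.5%, 6% and 7%.

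**Second set of assumptions.** True VE 40%, control rate 1.5 per year, shared multiplier for six weeks. For multipliers of 0.4, 0.7 and 1.5, VE as written within six weeks is 72%, 55% and 17%. With the shared function it is 38–40% throughout.

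**Heterogeneous exposure.** Same rate and true VE of 40%, gamma frailty with variance 1, no causal recency effect. As written, VE is 47% before any infection and 5–11% after one. With the shared function it is 29% and 21–25%. The shape is flatter, but 40% is not recovered.

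**The case against.** **The description is short and may be incomplete.** Analysis 4 does not write out X, γ, or U before a first infection. Z and γ are vectors in Section 8.5.1, and X may be time-dependent, so a recency term could have been meant in X or in Z = (1, R). It stands that the notation has room for the right model. But the text names Z as the indicator alone and puts recency nowhere else, so an analyst who follows it would fit the biased model.

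**N(t−) already adjusts for history.** If carried over from Analyses 1 and 2, it adjusts for how many infections, not how recent. In the table it is included, and large distortion remains.

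**Analyses 1 and 2 show recency by arm.** This stands in part. A reader might infer that nothing else in the SAP bears on the question; that is too strong, because the two curves can be compared by eye. No formal contrast of them is planned.

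**The remedy is partial.** This stands. A reader might infer that a main effect makes VE(u) unbiased. It does so only when children are otherwise alike. Time since infection is a post-randomisation variable, and with heterogeneous exposure the groups compared at a given u are selected.

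**It is exploratory.** This also stands. No primary endpoint, multiplicity set or significance rule in Sections 7.1 and 7.8 uses Analysis 4.

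**Conclusion.** The point holds for Analysis 4 as written and for its repetition in Section 8.6. Controls cannot show a recency effect, so one shared by both arms is reported as VE changing with time since infection. That conclusion needs only the SAP's equation and its definition of Z.

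The size is not known. It depends on the assumed recency effect, infection rate and VE, and the bias vanishes if recency has no effect in controls. The documents support a recency effect only in words, so the simulated figures are illustrations and not forecasts. Under them the error can be large: apparent VE of 60% or −12% shortly after infection when the truth is 30%.

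A reader might infer that the trial's main VE estimates are affected. They are not, because the primary analyses in Sections 7.5 and 7.6 do not use this model. For an exploratory analysis this is something that should be fixed, not a critical fault.

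**What to change.** Write out the full model for Analysis 4:

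- Once N_i(t−) is at least 1, set Z_i(t) = (1, RTS,S indicator). This gives a recency function γ1(u) shared by both arms and an RTS,S-by-recency function γ2(u), with VE(u) = 1 − exp{γ2(u)}. If a treatment term for all children also stays in X, VE(u) must be built from the sum of the two.
- Keep a separate RTS,S term for children not yet infected, and say how U is defined before a first infection.
- Test γ2(u) for constancy.
- Correct the comparison with Analysis 2, which uses RTS,S arms only.
- Make the same change for each haplotype in Section 8.6.
- Report VE(u) with the caveat that it conditions on post-randomisation infection history and may be distorted when exposure differs between children.

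The cost is more than a wording change: one more function to estimate, a rule for children not yet infected, and wider bands. There are only 300 controls, and Section 7.7.1 expects most participants to be infected by Month 20, so the group with no infection yet will be thin late in follow-up. The loss of precision has not been quantified here.
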